PROTOCOL TITLE: Hepatocyte Growth Factor to Improve Functioning in PAD:
The HI-PAD Study

PRINCIPAL INVESTIGATOR:

[name]
Division of General Internal Medicine and Geriatrics
Department Medicine
[contact]
[contact]

VERSION NUMBER: Version #19

VERSION DATE: 12/12/2022

OBJECTIVES & BACKGROUND:

Lower extremity peripheral artery disease (PAD) affects 10-15% of men and women age 65 and older and 15 to 20% of men and women age 75 and older (1-3). Older people with PAD have greater functional impairment, faster functional decline, and higher rates of mobility loss than people without PAD (1,4-10). Ischemia-reperfusion injury of calf skeletal muscle in PAD is associated with increased calf muscle oxidative stress and calf muscle fiber damage (11-15). We recently demonstrated impaired autophagy in calf muscle fibers from patients with PAD (16). Smaller size and reduced activity of calf muscle fibers are associated with greater functional impairment and increased mobility loss in people with PAD (16-20). However, no medical therapies have been identified that improve calf muscle perfusion or reverse skeletal muscle damage in people with PAD. Few medical therapies exist for improving functioning in PAD.

VM202 is a plasmid that contains cDNA and encodes two isoforms of hepatocyte growth factor (HGF) (21). VM202 is administered by injection into calf muscle where it locally produces HGF (21). HGF is a paracrine cellular growth factor that stimulates angiogenesis, promotes skeletal muscle regeneration, and improves autophagy (21-33). Preliminary evidence shows that VM202 improves the ankle brachial index (ABI), a measure of PAD severity, and promotes healing of lower extremity ulcers in PAD patients with critical limb ischemia (CLI) (21,34). We hypothesize that the favorable effects of HGF will improve walking performance and prevent functional decline in PAD patients age 55 and older without CLI.

Based on prior study (21,34), we will administer 4 mgs of VM202 or placebo to calf muscle of one or two legs (total up to 8 mgs per treatment) every 14 days for a total of four treatments. Our primary aim will test the hypothesis that VM202 improves six-minute walk performance in older PAD patients without CLI at six-month follow up. Our secondary aims will test the hypotheses that VM202 increases treadmill walking performance and calf muscle perfusion in older PAD patients. Our secondary aims will also test the hypotheses that VM202 improves calf muscle biopsy measures of capillary density, muscle regeneration, and autophagy. From this point forward, VM202 refers to the genomic cDNA hybrid of the HGF gene, which is the therapeutic intervention. The HI-PAD study will gather preliminary evidence to test our hypotheses. If our hypotheses are supported by this pilot study, results will be used to design a definitive randomized clinical trial of VM202 in older PAD patients without CLI.

SPECIFIC AIMS

Primary Aim. Among 36 PAD participants without critical limb ischemia (CLI), we will determine whether those randomized to unilateral or bilateral calf muscle VM202 injections have greater

improvement in the six-minute walk at six-month follow-up, compared to those randomized to calf muscle placebo injections. *We hypothesize that PAD participants randomized to VM202 will achieve greater increases or less decline in six-minute walk at six-month follow-up, compared to those randomized to placebo.*

Secondary Aim #1. Among 36 PAD participants without CLI, we will determine whether those randomized to unilateral or bilateral calf muscle VM202 injections have greater improvement in maximal and pain-free treadmill walking time, respectively, at 3-month follow-up, compared to those randomized to placebo. *We hypothesize that PAD participants randomized to VM202 will achieve greater increases or less decline in pain-free and maximal treadmill walking time at 3-month follow-up, compared to those randomized to placebo.*

Secondary Aim #2. Among 36 PAD participants without CLI, we will determine whether participants randomized to receive unilateral or bilateral calf muscle VM202 injections have greater increases in calf muscle perfusion, measured by magnetic resonance imaging (MRI) at baseline and 3-month follow-up, compared to those randomized to placebo injections. *We hypothesize that PAD participants randomized to VM202 will achieve more favorable changes in MRI-measured calf muscle perfusion at 3-month follow-up, compared to placebo.*

Secondary Aim #3. Among 36 PAD participants without CLI, we will use calf muscle biopsy at baseline and at 3-month follow-up to determine whether participants randomized to unilateral or bilateral calf muscle VM202 injections have more favorable changes in calf skeletal muscle markers of regeneration (satellite cell number and activation state and centrally nucleated and embryonic myosin heavy chain-expressing fibers), capillary density, and calf muscle markers of autophagy (LC3, LAMP2) compared to those randomized to unilateral or bilateral placebo injections. *We hypothesize that PAD participants randomized to VM202 will achieve more favorable changes in each skeletal muscle measure, compared to those randomized to placebo.*

Secondary Aim #4. Among PAD participants without critical limb ischemia (CLI), we will determine whether those randomized to unilateral or bilateral calf muscle VM202 injections have greater improvement in the walking impairment questionnaire (WIQ) and SF-36 physical functioning score (SF-36 PF) at 3-month and at 6-month follow-up, compared to those randomized to calf muscle placebo injections. *We hypothesize that PAD participants randomized to VM202 will achieve greater improvement in the WIQ and SF-36 at 3-month and at 6-month follow-up, compared to those randomized to placebo.*

Secondary Aim #5. Among 36 PAD participants without CLI, we will determine whether those randomized to VM202 injections have greater improvement in the six-minute walk at 3-month follow-up, compared to those randomized to placebo. *We hypothesize that PAD participants randomized to VM202 will achieve greater increases or less decline in the six-minute walk at 3-month follow-up, compared to placebo.*

Exploratory Aim. Among PAD participants without CLI, we will determine whether those randomized to VM202 injections have greater improvement in the six-minute walk at 12-month follow-up, compared to those randomized to placebo. *We hypothesize that PAD participants randomized to VM202 will achieve greater increases or less decline in the six-minute walk at 12-month follow-up, compared to placebo.*

INCLUSION AND EXCLUSION CRITERIA:

Inclusion criteria. All participants will be age 55 or above and will have PAD. All participants will have symptomatic PAD, defined as exertion-induced ischemic calf muscle symptoms during the six-minute walk, during the baseline exercise stress test, or during daily walking activities.

PAD will be defined as follows. First, an ankle brachial index (ABI) ≤ 0.90 at the baseline study visit is an inclusion criterion for PAD. Second, potential participants with an ABI > 0.90 who have vascular lab evidence of PAD or angiographic evidence of significant PAD may be eligible.

Exclusion criteria.

1. Above- or below-knee amputation.
2. Critical limb ischemia, including individuals with gangrene and lower extremity ulcers.
3. Wheelchair-bound or requiring a cane or walker to ambulate.
4. Walking is limited by a symptom other than PAD.
5. Planned lower extremity revascularization, major orthopedic surgery, or other major surgery during the next six months.
6. Lower extremity revascularization, orthopedic surgery, cardiovascular event, coronary revascularization, or other major surgery in the previous three months and planned revascularization or major surgery during the next six months.
7. Major medical illness including renal disease requiring dialysis, lung disease requiring oxygen, Parkinson's disease, or a life-threatening illness with life expectancy less than six months. [NOTE: Participants who only use oxygen at night may still qualify]
8. History of cancer within the last 5 years or incomplete cancer screening as recommended by the American Cancer Society. Specifically, participants will be asked to provide documentation regarding screening history for colon cancer and breast and cervical cancer (women), according to the American Cancer Society guidelines. Screening for colon cancer may consist of stool testing for blood in the past year. Men must either provide documentation regarding prostate cancer screening history or indicate after a telephone or in-person discussion with [name] that they have elected to decline prostate cancer screening. A chest computed tomography will be performed for participants 55 to 74 years old with ≥ 30 pack year history of smoking, unless they have not smoked within the past 15 years, to screen for lung cancer that may exclude them. The study team may also perform colon, breast, and/or cervical cancer screenings as part of study participation. The study team will provide stool testing for blood for colon cancer screening, mammogram for breast cancer screening, and a Pap test for cervical cancer screening according to the participant's eligibility for these screening tests, using the American Cancer Society guidelines. Men who elect to have prostate cancer screening who have not had this completed with their physician can have a prostate specific antigen (PSA) test performed by study investigators. Participants who have a history of non-melanoma skin cancer (i.e. basal cell carcinoma or squamous cell carcinoma of the skin) may still be eligible if the lesion was completely removed and there has been no evidence of recurrence in the past year.
9. Evidence of proliferative retinopathy. Participants who were treated for retinopathy at least 5 years prior to their baseline assessment who do not have evidence of proliferative retinopathy at the time of baseline assessment may still be eligible.
10. Positive test for active Human Immunodeficiency Virus (HIV), hepatitis B virus, hepatitis C virus or Human T-lymphotropic virus. Patients who have positive antibodies for HIV, hepatitis B, or hepatitis C who do not have detectable viral load will be eligible for participation.
11. Mini-Mental Status Examination (MMSE) score < 23 or dementia.
12. Participation in or completion of a clinical trial in the previous three months. [NOTE: after completing a stem cell or gene therapy intervention, participants will become eligible after the final study follow-up visit of the stem cell or gene therapy study so long as at least six months have passed since the final intervention administration. After completing a supplement or drug therapy (other than stem cell or gene therapy), participants will be eligible after the final study follow-up visit as long as at least three months have passed since the final intervention of the trial.]
13. Increase in angina or angina at rest.
14. Premenopausal women.

15. Non-English speaking.
16. Visual impairment that limits walking ability.
17. In addition to the above criteria, investigator discretion will be used to determine if the trial is unsafe or not a good fit for the potential participant.
18. Potential participants who have had symptoms from peripheral artery disease for less than six months will be excluded.
19. Potential participants who, after being advised of therapeutic options available for people with PAD, prefer to return to their physician to discuss alternative treatment (e.g. supervised exercise or revascularization). Potential participants may participate in the study after 12 weeks has passed since their last supervised exercise session or revascularization if they meet inclusion criteria.
20. Potential participants with a baseline six-minute walk value < 595 or $\geq 1,520$ feet will be excluded.
21. Potential participants with the following laboratory values will be excluded: a hemoglobin value < 8.0 g/dL, a white blood cell count $< 3,000$ cells per microliter, platelet count $< 75,000/\text{mm}^3$, GFR < 20 mL/minute/1.73 M², AST or ALT value > 3 times the upper limit of normal, or any other clinically significant laboratory abnormality which, in the opinion of the investigator, should exclude the participant. Participants may undergo a serum electrophoresis and an immunofixation blood test if indicated to further evaluate abnormalities on the complete blood count if needed to assess study eligibility.
22. Potential participants started on cilostazol within the past three months will be excluded. They may be evaluated for eligibility once three months has passed since beginning cilostazol.

Vulnerable populations (fetuses, pregnant women, children, prisoners, and institutionalized persons) and adults unable to consent will not be included in the study.

STUDY TIMELINES:

Each participant will participate in the study for six months after randomization. We plan to enroll 39 participants over an 18-month period.

STUDY ENDPOINTS:

Our primary outcome is change in the six-minute walk at six-month follow-up. We will repeat six-minute walk testing at 12-month follow-up to assess durability of VM202 benefit. Secondary outcomes are pain-free and maximal treadmill walking distance, calf biopsy measures of skeletal muscle regeneration, capillary density, and autophagy, the WIQ and SF-36 PF scores, and MRI-measured calf muscle perfusion at three-month follow-up.

Performance sites. Northwestern University Feinberg School of Medicine is the lead site. Performance sites also include University of Florida (Principal Investigator (PI) [name] MD), University of Kentucky (PI- [name]), and University of Virginia (PI- [name]). Drs. [name] and [name] will receive muscle specimens, labeled only with a study identification number, and will analyze them for our proposed muscle measures. [name] will receive de-identified magnetic resonance images labeled only with a study identification number, and will analyze them for perfusion measures.

PROCEDURES INVOLVED:

Initial eligibility criteria will be assessed by telephone. Potential participants who remain eligible after the telephone screening will be scheduled for a baseline visit, where they will undergo additional testing to determine their eligibility for randomization.

Baseline testing. Participants will provide informed consent at baseline. An ankle brachial index (ABI) will be performed. Questionnaires will be administered and physical functioning tests will be performed. A treadmill exercise stress test and a physical exam will be performed. A blood sample will be obtained and height and weight and vital signs will be measured. Participants will be asked to undergo an MRI but will remain eligible if they are unable or unwilling to participate in the MRI portion of the study. If the participant agrees to the optional muscle biopsy, they will be asked to undergo a biopsy and return approximately seven days afterward for an incision site check. Baseline testing will require testing at multiple visits performed over multiple days. Research procedures are described in more detail below.

Participants will receive written material about therapeutic options available for people with PAD, including supervised exercise and revascularization. Potential participants will be advised that if they would like to consider these alternative options, they should return to their physician to discuss the alternative therapeutic options before evaluation for the HI-PAD Study.

Randomization. Participants will be randomized to VM202 vs. placebo using a SAS program. We will use block randomization with block sizes randomly selected from 4 and 6.

Randomization will be stratified by:

1. Baseline functional performance, measured by a six-minute walk distance $\geq 1,100$ feet vs. $< 1,100$ feet.
2. Eligibility for unilateral vs. bilateral calf muscle injections.

VM202 and placebo. Participants randomized to VM202 will receive bilateral calf muscle injections of VM202 if both legs have an ABI value ≤ 0.90 . Participants randomized to placebo who have an ABI ≤ 0.90 in both legs will receive bilateral injections of placebo, containing no VM202. Participants who have an ABI ≤ 0.90 in only one leg will only receive injections in the leg with ABI ≤ 0.90 . Participants included based on angiographic evidence of PAD will have injections in both legs if there is significant angiographic atherosclerosis in both legs. If the angiographic evidence demonstrates atherosclerosis in one leg alone, then only the leg with significant atherosclerosis will receive injections. Participants who were eligible based on a toe-brachial index (TBI) will receive study drug injections in legs with a TBI ≤ 0.70

Injections of VM202 (0.50 mg/ml) or placebo are administered by a physician in a double-blinded fashion after randomization on Day 0, Day 14, Day 28, and Day 42, for a total of four treatment days. On each treatment day, 16 injections per leg will be administered. Each injection contains 0.5 ml of liquid. Each VM202 injection contains 0.25 mg of VM202. Therefore, participants randomized to VM202 will receive 4 mgs of VM202 per calf muscle on each treatment day. Note that only legs with an ABI < 0.90 will be eligible for injection.

Injection windows will be +/- three days relative to Days 14, 28, and 42. For example, Day 14 injections would ideally be given 11 to 17 days after Day 0. However, if a participant is not able to come in for the injections within this window, the injections may be given up until the day before the next scheduled injection. For example, Day 14 injections may be given up until Day 27. Day 42 injections may be given up to 14 days later (i.e. Day 56).

The following methods will be used to ensure that the correct legs are injected. First, prior to the procedure, the leg(s) eligible for injection will be selected by the study manager, based on the ABI value in each leg, and the designated leg(s) will be confirmed by a second coordinator. The leg(s) to be injected will be noted on the study medical record and a copy of the ABI data collection form will also be attached to the medical record. Second, the day of the injection visit, both the clinician performing the injections and a study coordinator will separately initial to

confirm the leg(s) eligible to inject. The clinician performing the injections will mark the skin of the leg to inject if only one leg is eligible.

Injections are placed beginning 2 cm below the popliteal crease, and are administered in a pre-designed sequence and pattern, at a measured distance 2 cm apart.

Placebo is composed of only the excipient buffer formulation minus the VM202. Placebo consists of sucrose: 55mg (1.1%) and sodium chloride: 45 mg (0.9%). The placebo is liquid and no reconstitution is necessary.

For the injections, the syringe gauge is 27. The depth of the injection is to muscle fascia (depending on body habitus, typically 8 to 14 mm below the injection site). Injection sites are into the medial and lateral gastrocnemius. Negative pressure is applied on the syringe to ensure that there is no blood return, in order to avoid intravascular injection.

Three-month follow-up testing. Participants will be asked to return to the medical center after three months to repeat some or all testing performed at baseline. The three month follow-up time point is relative to the date of the first injection (not relative to the dates of baseline testing). Follow-up testing will ideally be performed after three months +/- seven days relative to Day 0 injections. However, follow-up testing will be performed outside of this window if necessary. In all instances, follow-up testing will be performed as close to the target window (+/- seven days relative to day 0) as possible.

Six-month follow-up testing. Participants will return six months after receiving their first study injections to repeat some or all testing performed at baseline. Participants with diabetes mellitus will have a second retinal examination at six-month follow-up.

Twelve-month follow-up testing. Participants will return 12 months after receiving their first study injections for final follow-up testing. Some or all of the tests performed at baseline will be repeated.

Some or all study measures may be repeated at baseline or follow-up for data quality (e.g. if a treadmill test must be stopped due to extremely high blood pressure before the patient completed the test is one potential example of why a measure may need to be repeated). In some cases, it may be necessary to take an additional, unscheduled blood pressure measurement. For instance, if a participant has high blood pressure during the ABI and investigators would like to double check their arm pressure measurement before performing the six-minute walk either at the same visit or at a subsequent visit. Determinations about blood pressure checks will be made on a case-by-case basis in consultation with [name] or [name] or other qualified personnel.

Research procedures:

Ankle Brachial Index (ABI). After the participant rests supine for five minutes, the right brachial, dorsalis pedis (DP), posterior tibial (PT) and left DP, PT, and brachial artery pressures are measured using a hand-held Doppler probe. Pressures are measured twice. The ABI is calculated for each leg by dividing the average of the DP and PT pressures by the average brachial pressure. If an ankle brachial index result yields an equivocal result or suggests that a participant's lower extremity arteries are calcified, investigator discretion may be used to order a lower extremity artery test with toe pressures at Northwestern Memorial Hospital to determine eligibility for the trial. The test will repeat blood pressures in the arms and legs and will include a toe pressure measurement, which is performed by placing a small blood pressure cuff around

the great toe and attaching a plethysmography probe (circulatory sensor) on the bottom (ventral surface) of the tip of the great toe.

Questionnaire Administration. Participants will be administered IRB-approved study questionnaires by a trained and certified study coordinator.

Six-minute walk. In the six-minute walk, participants walk back and forth along a 100-ft hallway for six minutes after standardized instructions to complete as many laps as possible. Distance covered in six minutes is recorded.

Treadmill testing. The Gardner graded treadmill exercise test is used to measure change in maximal treadmill walking time. Speed is maintained at 2.0 miles per hour (mph) and treadmill grade increases by 2.0% every two minutes. If patients cannot walk at 2.0 mph, treadmill speed is started at 0.50 mph and increased by 0.50 mph every 2 minutes until the participant reaches 2.0 mph, after which the treadmill grade is increased every two minutes while the speed remains at 2.0 mph. Participants with an abnormal cardiac stress test may be allowed to participate in the study if they do not have symptoms of unstable angina and their physician agrees that it is safe for them to participate, or if they have another stress test with imaging (or a cardiac catheterization) that shows no evidence of ischemia. The treadmill test will be performed at baseline and 3-month follow-up.

Written Questionnaire Administration. Participants will be asked to complete the WIQ and the SF-36 physical functioning score at baseline and follow-up. These questionnaires will be self-administered.

Blood collection and long-term storage. Blood will be collected at baseline, Day 0 (first injection visit), 3-month follow-up, and 12-month follow-up. In addition, blood may be collected before and after one or more of the study injections (this additional blood testing was added to the protocol in July 2020). Please see the below table, "Schedule of Blood Test Evaluations", for specific tests that will be performed at each visit.

Blood drawn for long-term storage will be processed and stored at -70 degrees Celsius. Ten percent of participants will be randomly assigned a quality control ID within REDCap. These participants will have an extra set of blood drawn for quality assurance. Stored blood will await later analyses for biomarkers and other emerging blood markers related to peripheral artery disease that may change in response to the intervention. Samples will be labeled with the participant's study identification number and will not be stored with other health or identifying information. Information associated with the sample will be stored in a secure database on password protected computers that are secured by Northwestern University firewalls. Access is limited to study staff. If the samples are shared with other researchers not part of the current study, the PI will grant permission to the other researchers to analyze the samples. Samples will be identified with a study identification number and the other researchers will not have access to PHI. Results of testing on the blood samples will not be shared with the study participants.

Approximately 55 mls of blood will be drawn at baseline, 10 mls at Day 0, 60 mls at three-month follow-up, and 10 mls at 12-month follow-up. Additional blood may be drawn before and after each injection visit (Day 0, 14, 28, 42) for a total of 25 ml per injection visit to test for the presence of VM202. On Day 0, the total amount of blood drawn will be up to 35 ml (10 ml for comprehensive chemistry panel and CBC + up to 25 ml additional blood). Quality control participants will have an additional 25 mls of blood drawn at baseline and three-month follow-up.

Schedule of Blood Test Evaluations.

	Baseline	Day 0	Day 14	Day 28	Day 42	3-month follow-up	12-month follow-up
HemoglobinA1C	X	X				X	
HGF						X	
VM202		X*	X*	X*	X*	X	
HTLV, HIV-1, HIV-2, Hepatitis B, Hepatitis C	X						
Comprehensive Chemistry Panel	X	X				X	X
CBC	X	X				X	X
Long-term storage	X					X	

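### The injection rules for legs qualifying by angiography or toe-brachial index contradict the closing note that restricts injection to legs with ABI below 0.90

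*Combined protocol and SAP*

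**What the plan says.** All references are to the combined protocol and SAP.

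- **Inclusion criteria.** ABI ≤ 0.90 qualifies. In addition, "potential participants with an ABI > 0.90 who have vascular lab evidence of PAD or angiographic evidence of significant PAD may be eligible".
- **VM202 and placebo, ABI route.** Participants on VM202 receive "bilateral calf muscle injections of VM202 if both legs have an ABI value ≤ 0.90", and placebo follows the same rule. Those at or below 0.90 "in only one leg will only receive injections in the leg with ABI ≤ 0.90".
- **Same section, angiographic route.** Both legs are injected if both have significant atherosclerosis. "If the angiographic evidence demonstrates atherosclerosis in one leg alone, then only the leg with significant atherosclerosis will receive injections". No ABI condition is attached.
- **Same section, TBI route.** "Participants who were eligible based on a toe-brachial index (TBI) will receive study drug injections in legs with a TBI" of 0.70 or less. Again there is no ABI condition.
- **Same section, closing note.** "Note that only legs with an ABI < 0.90 will be eligible for injection".
- **Same section, correct-leg check.** The legs "will be selected by the study manager, based on the ABI value in each leg". The ABI form is attached to the record. TBI and angiography are not mentioned.
- **Randomization.** The second stratification factor is "Eligibility for unilateral vs. bilateral calf muscle injections".
- **MRI.** The cuff goes on the leg with the lowest ABI, and nothing requires that leg to be an injected one.
- **Calf muscle biopsies.** The biopsy is taken in the lowest-ABI leg and also 1 cm from an injection. The baseline biopsy precedes randomization, and the 3-month biopsy is taken beside its scar.

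**The concern.** The angiographic and TBI sentences are written without an ABI condition, and the inclusion criteria allow entry with ABI above 0.90. The note is exclusive and makes no exception for those routes. Staff who follow the note and staff who follow the route sentences would reach incompatible answers on whether a given calf may be injected. For some participants they would also differ on whether any stratum exists to randomize them in.

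The procedure meant to guarantee that the correct leg is injected does not settle this. For a participant who qualified by angiography or TBI, the ABI form does not hold the information that made the leg eligible.

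A secondary question follows. MRI and biopsy legs are chosen by lowest ABI, while injected legs may be chosen on other grounds. The measured leg and the injected leg could therefore differ. That would matter for Secondary Aims #2 (MRI perfusion) and #3 (biopsy measures), because the background section describes the plasmid as producing its growth factor locally in the injected muscle.

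**Working it through.** The plan gives no figure to reproduce on this point. The check applies each leg rule to the same patterns. **The ABI and TBI values below are assumed for illustration and are not trial data.**

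| Entry route | Leg 1 | Leg 2 | Injected under route rule | Injected under note (ABI < 0.90) | Lowest-ABI leg injected under route rule? |
|---|---|---|---|---|---|
| ABI | ABI 0.60 | ABI 1.05 | Leg 1 | Leg 1 | Yes |
| ABI | ABI 0.70 | ABI 0.90 | Both | Leg 1 | Yes |
| ABI | ABI 0.90 | ABI 1.05 | Leg 1 | None | Yes |
| Angiography, both legs diseased | ABI 0.95 | ABI 1.00 | Both | None | Yes |
| Angiography, leg 1 only diseased | ABI 1.00 | ABI 0.95 | Leg 1 | None | No |
| TBI | ABI 1.35, TBI 0.50 | ABI 1.10, TBI 0.85 | Leg 1 | None | No |
| TBI | ABI 1.35, TBI 0.50 | ABI 1.20, TBI 0.60 | Both | None | Yes |

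**Main contradiction (rows 4 to 7).** With ABI above 0.90 in both legs, the route rules give one or two legs and the note gives none. The unilateral/bilateral factor has no level for a participant with no eligible leg.

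**Inequality (rows 2 and 3).** The difference between ≤ and < has an effect only at exactly 0.90. In row 2 it would move the participant from the bilateral to the unilateral stratum.

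**Measured leg against injected leg.** If min(ABI leg 1, ABI leg 2) ≤ 0.90, the lowest-ABI leg itself meets the ABI rule and is injected, so no mismatch arises. A mismatch needs all four of these conditions:

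1. ABI above 0.90 in both legs.
2. Entry by angiography or TBI, with those rules followed over the note.
3. Injection in one leg only.
4. The lower ABI in the other leg.

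Rows 5 and 6 show that this can be reached. The MRI would then be of an uninjected calf. The biopsy could not be both in the lowest-ABI leg and 1 cm from an injection. The 1 cm rule points to an injected leg. But the baseline biopsy precedes randomization and fixes the later site, so the rule works only if the leg to be injected is designated by then.

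**Cost of a restricted analysis, if one is needed.** Take the plan's 36 participants, assumed split 18 and 18. The width of the 90% confidence interval for the difference is proportional to t(0.95, n1+n2−2) × √(1/n1 + 1/n2).

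- 18 and 18: √(1/18 + 1/18) = 0.3333.
- 17 and 18: √(1/17 + 1/18) = 0.3382. With the change in t the width ratio is 1.015.
- 17 and 17: ratio 1.031. 16 and 18: ratio 1.033.

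Dropping one participant therefore widens the interval by about 1.5%, and dropping two by about 3%. MRI and biopsy are optional, so 36 is a ceiling. With fewer participants measured, each exclusion would cost proportionately more.

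**The case against.** The strongest reply is that the note is shorthand for participants who entered by ABI. On that reading the route sentences stand and nobody is misdirected. The reading is possible, but the note does not say so, and the correct-leg check also speaks only of ABI.

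A second reply is that the conflict would surface before any harm. The stratum must be known before randomization, so staff facing a participant with no eligible leg under the note would have to stop and ask. This has force: silently injecting a different leg is less likely than an impasse. The wording still gives no answer once the question is asked.

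Several stronger readings are tempting, and the documents do not support them:

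- **That the stratum is generally misassigned.** In the main case the note yields no stratum, not the other one. A switch between strata is shown only at an ABI of exactly 0.90. The inequality deserves little weight, since a lost symbol in the text conversion cannot be excluded.
- **That the correct-leg check is a second, independent contradiction.** It states no cut-off and excludes no route. It is incomplete for the non-ABI routes.
- **That Aims #2 and #3 have lost power.** That would need a count of mismatched participants, which the documents do not give, and an assumption of no effect in an uninjected calf, which they do not establish. For biopsy, the 1 cm rule already points to an injected leg.
- **That the primary outcome is affected.** Nothing in the documents shows this.

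It is also fair to say that prospective changes come late. The SAP change text reports a review of randomized participants' baseline characteristics on 11/23/2022, so designating legs before baseline tests is probably no longer possible for most of them.

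**Conclusion.** The contradiction is real and lies in the text itself. For participants with ABI above 0.90 in both legs who enter by angiography or TBI, one section gives incompatible answers on which calves are injected, and no precedence is stated. This should be corrected. It is more than a missing detail, because following either rule literally breaks the other.

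The mismatch between measured and injected leg is a conditional gap. It needs four conditions together, cannot arise when either leg has ABI ≤ 0.90 and is injected under the ABI rule, and has not been shown to have occurred. On its own it would be minor.

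The number of participants affected by either part is unknown and may be zero. No loss of power and no effect on the six-minute walk are claimed. The main conclusion rests only on reading the note as written, without an implied exception.

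**What to change.** 1. Reconcile the three route rules, the closing note and the correct-leg check into one leg-eligibility rule. It should cover every entry route in the inclusion criteria and assign the unilateral/bilateral stratum. This review takes no view on which rule is right.
2. Reconcile the MRI and Calf muscle biopsies sections with that rule, including the two biopsy-site conditions.
3. From existing records, report which rule was applied, the number of participants by qualifying route (ABI, angiography, TBI), and any MRI or biopsy taken in a leg not designated for injection.
4. Only if that last count is above zero, add a sensitivity analysis for the affected aim, restricted to participants whose measured leg was designated for injection before randomization. A designation made at that point cannot depend on the assigned arm.

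The cost is wording in three sections, one count and one flag. If no measured leg is flagged, no further analysis is needed. If the sensitivity analysis is triggered, the price is a slightly smaller sample, with the interval widening shown in the working.
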